6.5.4.4 Immune-related adverse events

AEs associated with pembrolizumab exposure may represent an immunologic etiology. These immune-related AEs (irAEs) may occur shortly after the first dose or several months after the last dose of pembrolizumab treatment and may affect more than one body system simultaneously. IrAEs are thought to be caused by unrestrained cellular immune responses directed at the normal host tissues. Therefore, early recognition and initiation of treatment is critical to reduce complications. Based on existing pembrolizumab clinical study data, most irAEs were reversible and could be managed with interruptions of pembrolizumab and/or SAR444245, administration of corticosteroids and/or other supportive care.

Investigators must be extremely vigilant and be ready to intervene early in the management of irAEs because the onset of symptoms of irAEs (eg, pneumonitis) may be subtle. For suspected irAEs, adequate evaluation should be performed to confirm etiology or exclude neoplastic, infectious, metabolic, toxin, or other etiologic causes. Additional procedures or tests such as bronchoscopy, endoscopy, skin biopsy may be included as part of the evaluation. Based on the severity of irAEs, withhold or permanently discontinue pembrolizumab and administer corticosteroids.

SAR444245 may increase the incidence and severity of these events.

Dose modification and toxicity management guidelines for irAEs are provided in [Table 6](#). Of note, when study interventions are administered in combination, if the AE is considered immune-related, both drugs in the combination should be held according to recommended dose modifications. If a participant experiences several irAEs, the most conservative recommendation should be followed.

The CTCAE V5.0 must be used to grade the severity of AEs.

When pembrolizumab can be restarted, it should be administered at the initial planned dose and schedule as no modification is allowed:

- If the toxicity does not resolve or the criteria for resuming treatment are not met, the participant must be discontinued from all study drugs.
- If the toxicities do resolve and conditions are aligned with what is defined in [Table 6](#), the combination of SAR444245 or pembrolizumab may be restarted at the discretion of the investigator. In these cases where the toxicity is attributed to the combination or to SAR444245 alone, re-initiation of pembrolizumab as a monotherapy may be considered after communication with the Sponsor.

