Table 6 - Dose modification and toxicity management guidelines for immune-related AEs associated with pembrolizumab and SAR444245

General instructions:

1. Severe and life-threatening irAEs should be treated with IV corticosteroids followed by oral steroids. Other immunosuppressive treatment should begin if the irAEs are not controlled by corticosteroids.
2. Pembrolizumab and SAR444245 must be permanently discontinued if the irAE does not resolve or the corticosteroid dose is not \leq 10 mg/day within 12 weeks of the last pembrolizumab treatment.
3. The corticosteroid taper should begin when the irAE is \leq Grade 1 and continue at least 4 weeks.
4. If pembrolizumab and SAR444245 have been withheld, pembrolizumab and SAR444245 may be resumed after the irAE decreased to \leq Grade 1 after corticosteroid taper.

irAEs	Toxicity grade (CTCAE V5.0)	Action with pembrolizumab and SAR444245	Corticosteroid and/or other therapies	Monitoring and follow-up
Pneumonitis	Grade 2	Withhold ^a	Administer corticosteroids (initial dose of 1-2 mg/kg prednisone or equivalent) followed by taper.	Monitor participants for signs and symptoms of pneumonitis.
	Recurrent Grade 2, Grade 3 or 4	Permanently discontinue ^b	Add prophylactic antibiotics for opportunistic infections.	Evaluate participants with suspected pneumonitis with radiographic imaging and initiate corticosteroid treatment.
Diarrhea/Colitis	Grade 2 or 3	Withhold ^a	Administer corticosteroids (initial dose of 1-2 mg/kg prednisone or equivalent) followed by taper.	Monitor participants for signs and symptoms of enterocolitis (ie, diarrhea, abdominal pain, blood or mucus in stool with or without fever) and of bowel perforation (ie, peritoneal signs and ileus).
	Recurrent Grade 3 or Grade 4	Permanently discontinue ^b		Participants with \geq Grade 2 diarrhea suspecting colitis should consider GI consultation and performing endoscopy to rule out colitis. Participants with diarrhea/colitis should be advised to drink liberal quantities of clear fluids. If sufficient oral fluid intake is not feasible, fluid and electrolytes should be substituted via IV infusion.
AST or ALT elevation or Increased Bilirubin/hepatitis	Grade 2 ^c	Withhold ^a	Administer corticosteroids (initial dose of 0.5-1 mg/kg prednisone or equivalent) followed by taper.	Monitor with liver function tests (consider weekly or more frequently until liver enzyme value returns to baseline or is stable).

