
a SAR444245 to be withheld plus pembrolizumab to be withheld corresponds to "cycle delay".

b Permanently discontinuation of full study treatment.

c AST/ALT: >3.0 - 5.0 x ULN if baseline normal; >3.0 - 5.0 x baseline, if baseline abnormal; bilirubin:>1.5 - 3.0 x ULN if baseline normal; >1.5 - 3.0 x baseline if baseline abnormal.

d AST/ALT: >5.0 to 20.0 x ULN, if baseline normal; >5.0 - 20.0 x baseline, if baseline abnormal; bilirubin:>3.0 - 10.0 x ULN if baseline normal; >3.0 - 10.0 x baseline if baseline abnormal.

e AST/ALT: >20.0 x ULN, if baseline normal; >20.0 x baseline, if baseline abnormal; bilirubin: >10.0 x ULN if baseline normal; >10.0 x baseline if baseline abnormal.

f The decision to withhold or permanently discontinue pembrolizumab and SAR444245 is at the discretion of the investigator or treating physician. If control achieved or ≤ Grade 2, pembrolizumab and SAR444245 may be resumed.

g Events that require discontinuation include but are not limited to: encephalitis and other clinically important irAEs (eg. vasculitis and sclerosing cholangitis).

AE(s)=adverse event(s); ALT= alanine aminotransferase; AST=aspartate aminotransferase; CTCAE=Common Terminology Criteria for Adverse Events; DRESS=Drug Rash with Eosinophilia and Systemic Symptom; GI=gastrointestinal; ir=immune related; IV=intravenous; SJS=Stevens-Johnson Syndrome; T1DM=type 1 diabetes mellitus; TEN=Toxic Epidermal Necrolysis; ULN=upper limit of normal.

Note: Non-irAE will be managed as appropriate, following clinical practice recommendations.

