Immune-related Hepatitis	If any of the HECL criteria is met as defined in the protocol Section 8.3.8 Note: Immune-related hepatitis is a diagnosis made after excluding other possible etiologies such as viral flare, biliary or vascular obstruction, infection, medications, and alcohol use usually immune-related hepatitis response to dechallenge and/or steroids and re-occurs with rechallenge	Interrupt pembrolizumab and SAR444245 interventions for up to 12 weeks. Start IV corticosteroid 60 mg/day of prednisone or equivalent followed by oral corticosteroid. Monitor with biweekly laboratory tests, including AST, ALT, T Bili, D Bili, ALP, and INR. Restart pembrolizumab and SAR444245 intervention only if: Abnormal laboratory values resolve to Grade ≤ 1 or baseline (if abnormal at baseline) Taper steroid over 28 days Steroid treatment is tapered to prednisone <10 mg/day or equivalent Permanently fully Discontinue pembrolizumab and SAR444245 intervention if: Laboratory abnormalities do not resolve within 3 weeks Steroids cannot be lowered to ≤ 10 mg/day (or prednisone equivalent) within 12 weeks Decompensation to CP-C status
Other Causes	Rule out infection with blood, urine, and ascites culture - antibiotics should be started if infection is found If total bilirubin is elevated, imaging should be obtained to rule out vascular compromise, biliary obstruction, and/or tumor progression by imaging Ruled out alcohol use and hepatotoxic drugs including herbal and alternative medications	Restart pembrolizumab and SAR444245 only if laboratory values have returned to Grade 1 or baseline (if normal or Grade 1 at start) or to baseline grade within 3 weeks. If biliary obstruction is present, consultation with a gastroenterologist and/or an interventional radiologist should be obtained to see if the obstruction may be relieved.

Abbreviations: ALT= alanine aminotransferase; ALP=alkaline phosphatase; AST=aspartate aminotransferase; D Bili=direct bilirubin, HBe= hepatitis B e antigen; HBs= hepatitis B surface antigen; HBV= hepatitis B virus; HCV= hepatitis C virus; HECl= Hepatic Events of Clinical Interest; INR= international normalized ratio, IV=intravenous; T Bili=total bilirubin, TND= target not detected.

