8.3.8 Adverse event of special interest

Please refer to the master protocol.

Hepatic Events (HEs) include any of the following events if the events are considered not due to disease progression as judged by the investigator

- ALT:
 - a) Among subjects with Baseline ALT $<2 \times$ ULN: ALT $\geq 5 \times$ ULN
 - b) Among subjects with Baseline ALT $\geq 2 \times$ ULN: ALT $>3 \times$ the Baseline level
 - c) ALT >500 U/L regardless of baseline level
- Total Bilirubin:
 - a) Total bilirubin >3.0 mg/dL
- Regardless of laboratory values, hepatic decompensation diagnosed clinically, including:
 - New onset clinically detectable ascites requiring intervention for >3 days

- Hepatic Encephalopathy

In addition, symptomatic or asymptomatic overdose with pembrolizumab are described as below:

- An overdose of pembrolizumab will be defined as any dose of 1000 mg or greater.

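### Substudy 03 (Cohort C): for Grade 3-4 immune-related hepatitis, Table 6 requires permanent discontinuation while Table 9 allows interruption and restart, and no visible text says which governs

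*Protocol*

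**What the plan says.** All references are to substudy 03.

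**Table 6 (Section 6.5.4.4).** The relevant row is labelled "AST or ALT elevation or Increased Bilirubin/hepatitis". Grade 2 is withheld. Grade 3 or 4 is permanently discontinued, which footnote b explains as "Permanently discontinuation of full study treatment". Footnote d sets Grade 3 as "AST/ALT: >5.0 to 20.0 x ULN, if baseline normal; >5.0 - 20.0 x baseline, if baseline abnormal". For bilirubin, Grade 3 starts above 3 x ULN or above 3 x baseline on the same split. The starting corticosteroid dose at Grade 3-4 is 1-2 mg/kg prednisone or equivalent.

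**Table 9 (Section 6.5.4.7), immune-related hepatitis.** This row applies when any hepatic-event criterion of Section 8.3.8 is met and other causes have been excluded. One criterion reads "Among subjects with Baseline ALT $<2 \times$ ULN: ALT $\geq 5 \times$ ULN". The others are ALT above 3 x baseline when baseline is at least 2 x ULN, ALT above 500 U/L, total bilirubin above 3.0 mg/dL, and clinical decompensation. The instruction is "Interrupt pembrolizumab and SAR444245 interventions for up to 12 weeks. Start IV corticosteroid 60 mg/day of prednisone or equivalent". Both drugs may restart once values return to Grade 1 or below (or baseline) and steroids have been tapered. Permanent discontinuation applies if "Laboratory abnormalities do not resolve within 3 weeks", if steroids cannot be brought down within 12 weeks, or on decompensation to Child-Pugh C.

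**The concern.** One laboratory result in one participant leads to two incompatible instructions: stop both drugs for good, or interrupt and possibly rechallenge. A site that opens Table 6 and a site that opens Table 9 would each be following the protocol.

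The main stake is safety in a population with liver disease. Table 9 itself notes that immune-related hepatitis usually comes back on rechallenge. Exposure and discontinuation data for a 40-participant cohort would also depend on which table a site happened to use.

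**Working it through.** There is no plan figure to reproduce for this point. The check sets the two tables side by side, looks for a precedence rule, and then sizes the exposure.

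**1. Where the instructions collide (ALT).** Triggers come from Section 8.3.8 and grades from Table 6 footnote d. The baselines of 1.5 and 2 x ULN are illustrative.

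| Baseline ALT | Table 9 applies from | Table 6 Grade 3 starts | Conflict |
|---|---|---|---|
| Normal | 5 x ULN | above 5 x ULN | above 5 x ULN |
| 1.5 x ULN | 5 x ULN (5/1.5 = 3.3 x baseline) | above 5 x 1.5 = 7.5 x ULN | above 7.5 x ULN |
| 2 x ULN | above 3 x 2 = 6 x ULN | above 5 x 2 = 10 x ULN | above 10 x ULN |

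Below the conflict range the event is Grade 2 in Table 6, which withholds and may resume, so the tables agree on not stopping permanently. The 500 U/L criterion can bring Table 9 in earlier but does not move the lower edge of the conflict. The ULN in U/L is not given.

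For bilirubin with normal baseline, Table 6 Grade 3 starts above 3 x ULN. Assuming a ULN of 1.0-1.2 mg/dL, that is above 3.0-3.6 mg/dL, so every such Grade 3 value also meets the Section 8.3.8 criterion of more than 3.0 mg/dL. An isolated AST rise is not a Section 8.3.8 criterion and does not by itself bring Table 9 in.

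Table 9's list of reasons for permanent discontinuation contains no grade. A Grade 4 ALT (above 20 x ULN with normal baseline) that resolves in time may therefore restart under Table 9 and may not under Table 6.

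**2. Is there a precedence rule?**
- Section 6.5.4.7 introduces Table 9 as additional guidance for HCC participants and does not say that it replaces Table 6.
- Appendix 11 (Table 13) sends liver enzyme increases to Table 6.
- The Table 6 row in this substudy names hepatitis. The corresponding rows in substudies 02 and 04 do not. Table 6 here expressly covers the diagnosis.
- Section 6.5.3 carves out only events in Tables 3-8, so Table 9 is not on its list.
- Section 6.5.4.4 says "If a participant experiences several irAEs, the most conservative recommendation should be followed", and Section 6.5.1 has a similar rule for several toxicities. Neither addresses one event under two tables.

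**3. Steroid start.** Table 9's 60 mg/day lies within 1-2 mg/kg for body weights from 60/2 = 30 kg to 60/1 = 60 kg. Above 60 kg it is below the Table 6 range.

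**4. Frequency.** Table 13 gives pembrolizumab hepatitis at 0.5% for Grade 3 and 0.1% for Grade 4, together 0.6%. With n = 40 (Section 9.2):

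P(at least one) = 1 - (1 - 0.006)^40 = 1 - 0.994^40 = 0.214, about 21%.

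Each affected participant is 1/40 = 2.5% of the cohort.

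**5. Table 9's time limits.** Laboratory resolution by day 21 plus a 28-day taper starting at resolution ends by day 21 + 28 = 49, inside the 12-week (84-day) limit.

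**The case against.** The best defence is that Table 9 is the HCC-specific text, so it should be read as governing. These tables are also headed as guidelines, and Section 6.5.3 leaves the final dose-modification decision to the Investigator. The specific-over-general reading is plausible but not stated, and Table 13 points the other way. Investigator judgment does not supply a default. Section 6.5.1 asks for Sponsor consultation on departures from the protocol, and a site cannot tell which table it would be departing from. One reservation stands: the master protocol is not in the text available here, so a precedence rule there cannot be ruled out.

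Four stronger readings are tempting, and the documents do not support them.

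- A reader might infer that Table 9 contradicts itself, with 3 weeks against 12. The 3 weeks govern laboratory resolution, while the 12 weeks govern the interruption and the steroid reduction. As shown above, both can be met.
- A reader might infer that every ALT above 5 x ULN is caught. That is true only with a normal baseline, and the protocol anticipates abnormal baselines in this cohort.
- A reader might infer that applying the more conservative rule leaves Table 9's restart route unusable. It remains usable for Table 9 events that are Grade 2 in Table 6, for example ALT between 3 and 5 x baseline when baseline is at least 2 x ULN.
- A reader might size the problem from the 1-2% hepatitis rate in Section 6.5.4.7, which gives 1 - 0.99^40 = 33% to 1 - 0.98^40 = 55%. That rate is not restricted to Grade 3-4, where the tables conflict.

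**Conclusion.** The contradiction is real and bears on a stopping rule. For immune-related hepatitis that is Grade 3-4 in Table 6 and meets a Section 8.3.8 criterion, the substudy gives two incompatible instructions and no visible way to choose between them. The difference in starting steroid dose is secondary but belongs to the same reconciliation.

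The chance that the conflict arises at least once in Cohort C is about 21%. This assumes 40 treated participants, independence between them, and the protocol's pembrolizumab Grade 3-4 rate carried over to this population. Section 6.5.4.4 says SAR444245 may increase incidence and severity but gives no figure, so the true chance could be higher.

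An effect on ORR should not be read into this. Stopping treatment does not in itself reclassify a response, and each participant accounts for at most 2.5 percentage points. The case for correction rests on participant safety and consistent conduct across sites.

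**What to change.** In the next substudy 03 amendment, reconcile Tables 6 and 9 and state which one governs immune-related hepatitis in Cohort C. Then align the text that depends on that choice: the table list in Section 6.5.3, the liver-enzyme pointer in Appendix 11 (Table 13), and the steroid starting dose in whichever table is subordinate.

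One small gap can be closed at the same time. Table 9 requires prednisone below 10 mg/day for restart but discontinues only if 10 mg/day or less is not reached, so exactly 10 mg/day meets neither condition.

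The choice of clinical rule belongs to the sponsor's hepatology and safety leads, and none is proposed here. The cost is a text correction and its communication to sites, with no change to data collection.

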6.6 CONTINUED ACCESS TO INTERVENTION AFTER THE END OF THE STUDY

Please refer to the master protocol.

6.7 TREATMENT OF OVERDOSE

Please refer to the master protocol for definition and treatment of SAR444245 overdose.

An overdose of pembrolizumab will be defined as any dose of 1000 mg or greater. There is no specific antidote for overdose with pembrolizumab. No specific information is available on the treatment of overdose of pembrolizumab. In the event of overdose, the participant should be observed closely for signs of toxicity. Appropriate supportive treatment should be provided if clinically indicated.

6.8 CONCOMITANT THERAPY

Please refer to the master protocol.

7 DISCONTINUATION OF STUDY INTERVENTION AND PARTICIPANT DISCONTINUATION/WITHDRAWAL

7.1 DISCONTINUATION OF STUDY INTERVENTION

Please refer to the master protocol.

7.2 PARTICIPANT DISCONTINUATION/WITHDRAWAL FROM THE STUDY

Please refer to the master protocol.

7.3 LOST TO FOLLOW UP

Please refer to the master protocol.

8 STUDY ASSESSMENTS AND PROCEDURES

[figure not shown]
Please refer to the master protocol and [Section 1.3](#).

8.1 EFFICACY ASSESSMENTS

Please refer to the master protocol.

8.1.1 Assessment of objective response using the most appropriate modality according to the nature of the measurable lesion(s)

Please refer to the master protocol for RECIST 1.1.

8.2 SAFETY ASSESSMENTS

Please refer to the master protocol.

In addition, combining SAR444245 with other anticancer therapies may increase the frequency and severity of immune-related adverse events related to other anticancer therapies. Immune-mediated endocrinopathies involving the thyroid being the most frequent, T3, T4, TSH, and cortisol level will be monitored.

8.3 ADVERSE EVENTS (AES), SERIOUS ADVERSE EVENTS (SAES) AND OTHER SAFETY REPORTING

Please refer to the master protocol.

8.3.1 Time period and frequency for collecting AE and SAE information.

Please refer to the master protocol for AEs and serious adverse events (SAEs) collection. For participants in Cohort C irAEs will be collected until 90 days following last administration of study treatment regardless of whether or not another anticancer therapy is initiated.

8.3.2 Method of detecting AEs and SAEs

Please refer to the master protocol.

8.3.3 Follow-up of AEs and SAEs

Please refer to the master protocol.

8.3.4 Regulatory reporting requirements for SAEs

Please refer to the master protocol.

For pembrolizumab, SAEs that are considered expected will be specified in the reference safety information (country-approved product labeling for pembrolizumab).

8.3.5 Pregnancy

Please refer to the master protocol.

8.3.6 Cardiovascular and death events

Please refer to the master protocol.

8.3.7 Disease-related events and/or disease-related outcomes not qualifying as AEs or SAEs

Not applicable.

8.3.8 Adverse event of special interest

Please refer to the master protocol.

Hepatic Events (HEs) include any of the following events if the events are considered not due to disease progression as judged by the investigator

- ALT:
 - a) Among subjects with Baseline ALT $<2 \times$ ULN: ALT $\geq 5 \times$ ULN
 - b) Among subjects with Baseline ALT $\geq 2 \times$ ULN: ALT $>3 \times$ the Baseline level
 - c) ALT >500 U/L regardless of baseline level
- Total Bilirubin:
 - a) Total bilirubin >3.0 mg/dL
- Regardless of laboratory values, hepatic decompensation diagnosed clinically, including:
 - New onset clinically detectable ascites requiring intervention for >3 days

- Hepatic Encephalopathy

In addition, symptomatic or asymptomatic overdose with pembrolizumab are described as below:

- An overdose of pembrolizumab will be defined as any dose of 1000 mg or greater.

8.3.9 Guidelines for reporting product complaints

Please refer to the master protocol.

8.4 PHARMACOKINETICS

Please refer to the master protocol.

8.5 GENETICS AND/OR PHARMACOGENOMICS

Please refer to the master protocol.

8.6 BIOMARKERS

Please refer to the master protocol.

For participants to Cohort C (HCC), tumor biopsy is optional.

8.7 IMMUNOGENICITY ASSESSMENTS

Please refer to the master protocol.

8.8 HEALTH ECONOMICS

Please refer to the master protocol.

8.9 USE OF BIOLOGICAL SAMPLES AND DATA FOR FUTURE RESEARCH

Please refer to the master protocol.

9 STATISTICAL CONSIDERATIONS

9.1 STATISTICAL HYPOTHESES

Please refer to the master protocol.

9.2 SAMPLE SIZE DETERMINATION

The plan is to treat approximately 40 participants in Cohort C.

Table 10 lists estimated ORR and 90% exact confidence intervals (CIs) by number of responders from a sample size of 40 participants treated.

Table 10 - Estimated objective response rate (ORR) depending on number of responders

Number of Responders (N=40)	Objective Response Rate in % (90% Clopper-Pearson CI)
2	5% (0.9% - 14.9%)
4	10% (3.5% - 21.4%)
6	15% (6.7% - 27.5%)
8	20% (10.4% - 33.2%)
10	25% (14.2% - 38.7%)
12	30% (18.3% - 44.0%)
14	35% (22.6% - 49.2%)

CI: confidence interval; N=number.

With a sample size of 40 study participants, the probability of observing 1 or more instances of a specific AE with a true incidence rate of 1%, 2%, or 5% is 33.1%, 55.4%, or 87.1%, respectively. This provides reasonable assurance that events occurring at $\geq 5\%$ frequency can be identified in this cohort.

9.3 POPULATIONS FOR ANALYSES

Please refer to the master protocol.

9.4 STATISTICAL ANALYSES

Please refer to the master protocol.

9.4.1 General considerations

Please refer to the master protocol.

9.4.2 Primary endpoint(s)

Please refer to the master protocol.

9.4.3 Secondary endpoint(s)

Please refer to the master protocol.

9.4.4 Tertiary/exploratory endpoint(s)

[REDACTED]

9.4.4.1 Exploratory antitumor indicators

[REDACTED]

9.4.5 Other safety analysis

Please refer to the master protocol.

9.4.6 Other analysis

Please refer to the master protocol.

9.5 INTERIM ANALYSES

Please refer to the master protocol.

If the predictive probability of concluding a minimum clinical meaningful effect of the study treatment (ORR of 5%) at the end of study is <15%, the corresponding cohort will be stopped for futility. To facilitate the calculation of predictive probability, a minimum informative prior of Beta (0.5, 0.5) is used at the time of the design of the study. However, emerging data generated from outside of the study may warrant a different prior to be considered before this interim analysis.

